12 OUTCOME DETERMINATIONS

Aim 1. Determine the efficacy of peripheral, central, and combined treatments in alleviating pain among women with VBD-p and VBD-c.

Primary Endpoints:

- Ia. pain score during tampon test at 16 weeks
- Ib. self-reported pain *via* SF-MPQ at 16 weeks

Secondary Endpoints:

- Ila. experimental pain *via* local and remote PPTs at 16 weeks
- Ilb. COPC pain levels *via* COPC follow-up survey at 16 weeks
- Ilc. Pain scores and PPTs at 8 weeks and 24 weeks

Aim 2. Determine the efficacy of peripheral, central, and combined treatments in improving patient reported outcomes among women with VBD-p and VBD-c.

Primary Endpoints:

- Ia. self-reported physical/mental health *via* SF12v2 at 16 weeks
- Ib. sexual health *via* PROMIS at 16 weeks

Secondary Endpoints:

- Ila. mood *via* SCL-27 at 16 weeks
- Ilb. somatic awareness *via* PILL at 16 weeks
- Ilc. perceived stress *via* PSS at 16 weeks
- Ild. sleep *via* sleep scale at 16 weeks
- Ile. Patient reported outcomes at 8 weeks and 24 weeks

Aim 3. Determine the efficacy of peripheral, central, and combined treatments in normalizing cytokine and microRNA expression profiles in vaginal and blood tissues collected from women with VBD-p and VBD-c.

Primary Endpoints:

- Ia. cytokine levels *via* mesoscale discovery assays at 16 weeks
- Ib. microRNA levels *via* sequencing read at 16 weeks

Secondary Endpoints:

- Ila. cytokine and microRNA levels at 8 weeks and 24 weeks
- Ilb. Aim 3 will also identify cytokine and microRNA biomarkers at baseline that predict treatment response at 8, 16, and 24 weeks

13 METHODS TO PROMOTE ADHERENCE

Protocol training and adherence will be a major focus of the training for all Investigators, research nurses, and other essential personnel. An initial training session will take place prior to beginning recruitment in order to instruct and calibrate study personnel on all aspects of vulvar exam, QST, sample collection/processing, etc. Adherence will then be maintained by continuing to review study procedures during weekly calls and by annual follow-up training sessions (in-person at the UNC Hillsborough clinic site with a Skype connection to the UCLA clinic site). In addition, the CC will contact each site to offer per-participant feedback on adherence; will review episodes of non-adherence and reemphasize the importance of adherence; and will provide adherence reports.

14 PARTICIPANT SAFETY AND ADVERSE EVENTS

14.1 Single IRB

Our clinical trial will comply with the NIH Policy on the Use of a Single Institutional Review Board (sIRB) for Multi-Site Research (NOT-OD-16-094), with the goal to eliminate duplicative IRB review and streamline the IRB review process so that research can proceed as effectively and expeditiously as possible. The Duke University IRB will serve as the sIRB of record. UCLA and UNC will serve as participating sites and have agreed to rely on the proposed sIRB. Duke University will be responsible for maintaining records of the authorization/reliance agreements and of the communication plan. This agreement, clarifying the roles and responsibilities of the sIRB and participating sites, will be signed by all participating sites prior to initiating the study.

Communication between Duke, UCLA, UNC and the sIRB will be managed by the CC. The CC will assist with the development of IRB protocols, participant randomization, data management, safety surveillance, and medical communications.

14.2 Definitions

14.2.1 Adverse Events

An adverse event (AE) is defined as any untoward medical occurrence with the use of a drug in a subject whether or not considered drug or biologic related. An AE can therefore be any unfavorable and unintended sign, symptom, or disease temporarily associated with the use of a pharmaceutical product or biologic.

The study is limiting collection of AEs to focus on potential impacts of the blinded study medication. Only the following AEs will be documented in the electronic Case Report Form (eCRF):

- Swelling
- Burning
- Blistering
- Drowsiness
- Difficulty sleeping (insomnia)
- Cloudy thinking
- Dry mouth
- Nausea
- Vomiting
- Loss of appetite
- Weight gain
- Weight loss
- Anxiety
- Hives
- Rash
- Difficulty urinating
- Constipation
- Vision changes
- Breast swelling
- Decreased sexual drive

- Low blood sugar
- High blood sugar
- Increased heart rate
- Irregular heartbeat
- Suicidal thinking
- Mania
- Agitation
- Hallucinations
- Muscle tremor
- Muscle rigidity
- Seizures
- Bone pain

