8.2 Potential Side Effects and Risk Reduction Plan

Expected risks associated with lidocaine/estradiol compound cream include an adverse reaction to either medication or the compounded base. Lidocaine is well tolerated and safe, particularly with topical administration in small doses which significantly reduces the risk of lidocaine toxicity. The proposed daily dose is extremely small, with minimal systemic uptake when used as instructed. As with any medication, participants will be clearly instructed to use as directed. Significant over-usage would be required to approach toxicity. This is extremely rare in clinical practice. The medication will not be used in women with prior sensitivity or allergy to local anesthetics. A mild burning or tingling sensation with application is typical and resolves once the anesthetic takes effect. There is a rare risk of erythema, burning or blistering at the application site. The lidocaine will be compounded in a hydrophilic petrolatum, an inert and well-tolerated compounding cream. The second component of this compounded cream is estradiol. Like the lidocaine, women with prior sensitivity to this medication should not be enrolled, as well as women who have contraindications to topical estrogen therapy. The topical application has very low systemic uptake (0.01% per ½ gram dose), is well-tolerated and safe in reproductive-aged women. Women with potential contraindications to systemic estrogen, such as those with breast cancer, stroke or coronary artery disease, may still receive topical estrogen due to the extremely low absorption rate. In these cases, the treating physician will be contacted for permission to participate in the study, as is the protocol with clinical use of topical estrogen. Participants will be

instructed to notify the research team if they experience any adverse reaction.

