Nortriptyline, a second-generation tricyclic antidepressant, with few associated risks is well-tolerated when compared to other agents in this pharmacologic class. The medication will be administered at night to minimize symptoms but it has the effect of insomnia, participants may switch to morning administration. The maximum dose of this medication is 150 mg/day for major depression, but is efficacious at lower doses for the management of pain disorders. This medication should not be used in participants with: homicidal or suicidal ideations, in the acute recovery phase of a myocardial infarction (due to risk of arrhythmia), epilepsy, or acute angle glaucoma. Expected side effects with nortriptyline include drowsiness, difficulty sleeping (insomnia), cloudy thinking, and dry mouth. Other potential side effects include nausea, vomiting, loss of appetite, weight gain/loss, anxiety, hives/rash, delayed micturition, urinary retention, constipation, vision changes, breast swelling, decreased sexual drive, hyper/hypoglycemia, tachycardia or irregular heartbeat. Risk of serotonin syndrome is increased when participants are taking other serotonergic medications in addition to nortriptyline. Risk of long QT syndrome is increased when participants are taking citalopram or escitalopram. If the potential participant endorses either taking two or more serotonergic antidepressant medications or taking either citalopram or escitalopram, then the study MD will consult with the prescribing provider to determine if it would be safe for the potential participant to take nortriptyline in this clinical trial. Since serotonin syndrome is most likely to occur within 24 hours of starting/increasing the dosage of a serotonergic medication, the researcher will attempt to contact randomized participants within 24 hours of starting/increasing nortriptyline doses if the participant is taking other serotonergic antidepressants.

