14.2.2 Serious Adverse Events

A serious adverse event (SAE) is an AE that results in the following outcomes:

- Death
- Life-threatening AE: Places the subject at immediate risk of death at the time of the event as it occurred. It does not include an AE that, had it occurred in a more severe form, might have caused death.
- Persistent or significant incapacity or substantial disruption of the ability to conduct normal life functions.
- Inpatient hospitalization or prolongation of hospitalization.
- Congenital anomaly or birth defect.
- Important medical events that may not result in death, be life threatening, or require hospitalization may be considered a serious adverse event when, based upon appropriate medical judgment, they may jeopardize the subject and may require medical or surgical intervention to prevent one of the outcomes listed in this definition above.

This determination is based on the opinion of the investigator.

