14.2.4 Recording and Reporting of Adverse Events

The site investigator is responsible for monitoring the safety of participants enrolled into the study at the study sites. The investigator will probe, via discussion with the participant, for the occurrence of AEs during each study visit and record the information in the site's source documents. Participants will be instructed to report the occurrence of potential AEs between visits (on a weekly basis) using the Electronic Data Capture (EDC) system. The investigator will receive an email notification and will call the participant to gather further information about the AE(s).

The investigator will record selected AEs on the eCRF. Adverse events will be described by duration (start and stop dates), severity, outcome, and relationship to study drug. Adverse events will be reported to the Data Safety Monitoring Board (DSMB), Duke IRB and/or other agencies according to guidelines established by those entities/agencies. All AEs that are identified, whether or not listed in Section 14.2.1, will be followed by the site until resolution or stabilization. Adverse Events will be captured from the time of consent through the Month 6 visit.

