14.3 Data Safety Monitoring Board

The DSMB will be composed of 4 members: a physician, a statistician, a patient representative, and a bioethicist. All DSMB operations will be managed by the DCRI.

The goal of the DSMB will be to monitor patient safety and to review the performance of the study. The DSMB will be responsible for providing recommendations regarding trial's conduct and guidance to ensure the safety and well-being of patients treated by study physicians. A separate DSMB charter will outline the operating guidelines for the committee, the protocol for evaluation of data, and data tables to be provided. The charter will be created prior to study enrollment and agreed upon during the initial meeting of the DSMB. It is anticipated that the DSMB will meet at 6-month intervals to review the accumulating data for safety.

DSMB Analyses: A DCRI Statistical Analyst and Programmer will generate the analyses required by the DSMB charter and provide these in advance of each DSMB meeting. This individual will ensure high quality and timely reports are submitted. Confidential Interim Data Reports will be prepared regularly by the DSMB statistician as specified in the Charter. The report will include recruitment and retention rates, SAEs, and other information as requested by the DSMB Chair.

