15.5 Analysis of Safety Data and Statistical Monitoring Plan

Interim data analysis for efficacy and futility will not be conducted due to relatively small size and short duration of this clinical trial. Safety data, summarized at the treatment level, will be assessed approximately every 6 months by the DSMB. Adverse Events will be summarized by treatment group and will include incidence by term, severity, relationship to study medication as well as overall incidence rates (regardless of severity and relationship to study medication).

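### As written, a serious adverse event from a cause outside the closed 32-term list has no stated route into the study database or the Section 15.5 safety summaries

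*Combined protocol and SAP*

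**What the plan says.** Section 14.2.1 gives the reason for restricting collection: "The study is limiting collection of AEs to focus on potential impacts of the blinded study medication". It then sets the rule: "Only the following AEs will be documented in the electronic Case Report Form (eCRF". A list of symptoms follows, with no entry for other events.

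Section 14.2.2 places serious events inside the restricted class: "A serious adverse event (SAE) is an AE that results in the following outcomes". The outcomes include death, a life-threatening event and hospitalisation. The section gives no separate SAE form, eCRF page or reporting timeline.

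Section 14.2.4 repeats the limit: "The investigator will record selected AEs on the eCRF". It also has sites note AEs in source documents at each visit, follow unlisted AEs to resolution or stabilisation, and report AEs to the DSMB, the IRB and other agencies under the guidelines of those bodies. Participants report possible AEs weekly through the electronic data capture system, which prompts a call from the investigator.

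Section 14.3 says of the interim report: "The report will include recruitment and retention rates, SAEs, and other information as requested by the DSMB Chair". Section 15.5 plans AE summaries by treatment group, by term, severity and relationship, together with "overall incidence rates (regardless of severity and relationship to study medication". It names no SAE table.

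**The concern.** A closed list of expected side effects is a defensible way to reduce the burden of recording minor events. It is a poor filter for serious events, because the serious event that matters most may be one that nobody listed. Here the rule says *only*, the definition makes every SAE an AE, and no sentence takes SAEs out of the rule. A coordinator who applies the text literally would have no eCRF term for an infarction, a stroke, a thrombosis or a syncope, or for a hospitalisation or death from any other unlisted cause.

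The final between-arm safety comparison is at stake. If it is drawn from the eCRF, unlisted serious events would be missing from every arm, and a figure described as overall incidence would be the incidence of 32 pre-chosen terms. The topic is not remote for this trial. Section 8.2 discusses arrhythmia risk with nortriptyline, and allows that women with a history such as stroke or coronary artery disease may receive the topical estrogen with their physician's permission.

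A lesser matter is that some risks named in Section 8.2 have no term of their own on the list.

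**Working it through.** The plan states no figure on this point, so there is none to reproduce. The check is a count, a mapping and a comparison of sections.

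**1. Size of the list (Section 14.2.1).** The list is printed in two blocks, of 20 and 12 terms: 20 + 12 = 32, all distinct. None is a catch-all.

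**2. Route of an off-list SAE, section by section.**

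| Section | What it provides for an SAE from an unlisted cause |
|---|---|
| 14.2.1 | Not on the list, so not documented in the eCRF |
| 14.2.2 | Still an AE by definition; no exemption from the list |
| 14.2.4 | Source-document note, follow-up, and reporting to DSMB/IRB under their guidelines; eCRF entry for selected AEs only |
| 14.3 | SAEs are a named item of the DSMB report; data source not stated |
| 15.5 | AE summaries by group; no SAE table; data source not stated |
| 16.1 | Site staff enter all study data into REDCap; data are exported from there to SAS for summary and analysis |

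Section 16.1 settles the source for the final analysis: the tables come from what sites enter in REDCap. Sections 14.2.1 and 14.2.4 do not let an unlisted event be recorded on the AE form there. So no route into the Section 15.5 summaries is stated for it. Section 14.3 nevertheless promises SAEs without limiting them to listed terms, and the two cannot both be met from the eCRF as described.

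**3. Death and hospitalisation.** Section 14.2.2 treats these as outcomes of an AE, and Section 14.2.4 records an outcome for each recorded AE. A listed event that leads to hospitalisation is therefore captured. The gap concerns unlisted causes only.

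**4. Risks named in Section 8.2 against the list.** Separating the side effects and risks in Section 8.2 gives 29 items. Of these, 24 map to a list term and 29 − 24 = 5 do not: tingling, erythema, lidocaine toxicity, serotonin syndrome and long QT. Two of the relevant statements are "There is a rare risk of erythema, burning or blistering at the application site" and "Risk of long QT syndrome is increased when participants are taking citalopram or escitalopram". Burning and blistering are listed but erythema is not. Serotonin syndrome is partly covered by agitation, hallucinations, muscle tremor, muscle rigidity and increased heart rate, and long QT partly by irregular heartbeat. The denominator of 29 depends on how synonyms are split or merged.

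**5. How likely such an event is (illustration only).** With 400 women allocated 1:1:1:1, each arm has 400/4 = 100, and each active component is given in two arms, so to 200 women. The documents give no rate of unlisted SAEs. Assume a risk p of 0.5% to 1% per woman:

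- P(at least one among 200) = 1 − (1 − p)^200
- p = 0.005: 1 − 0.995^200 = 0.63; expected number 200 × 0.005 = 1
- p = 0.01: 1 − 0.99^200 = 0.87; expected number 200 × 0.01 = 2

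Under these assumed risks, at least one such event is more likely than not. The figures do not measure harm.

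**The case against.** A reader might infer that unlisted SAEs never reach the DSMB or any safety table. The documents do not support that. Section 14.3 names SAEs as an item of the DSMB report, and Section 14.2.4 sends AEs to the DSMB and IRB without confining them to listed terms. Sections 14.3 and 17.1 leave the DSMB's data tables to a charter that is not among the documents, and the charter may set up a separate SAE channel.

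A reader might also take it as settled that the authors meant the list to govern serious events. No sentence says so. The sections could be read as focused collection of ordinary AEs, with SAEs handled separately. What weakens this reading is that no separate handling is described, while the restriction is explicit and the definition makes an SAE an AE.

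Nor can it be said that nothing unlisted ever enters an electronic system. The weekly participant report goes through the EDC, and the text does not limit it to listed terms. But it is an alert that leads to a call, after which only selected AEs go on the eCRF. It is not a structured SAE record, and it cannot be relied on for a participant who has died or is incapacitated.

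Two further objections stand. Most risks in Section 8.2 are on the list, and the schedule in Appendix A includes no ECG, so a long QT term would depend on a diagnosis made outside the study; the missing terms are a secondary matter. And with one or two expected events per 200 women under the assumed risks, no between-arm imbalance could be shown statistically even with full capture. The case for capture is that individual serious events should be visible and attributable to an arm. It does not rest on power to compare rates.

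**Conclusion.** The concern holds in a limited form. Followed as written, Sections 14.2.1, 14.2.2 and 14.2.4 leave an SAE from an unlisted cause with no stated route into the study database, and hence none into the Section 15.5 summaries. They also conflict with the promise in Section 14.3. This comes from a stated rule, so it is more than missing detail. The sections need to be reconciled.

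The size is structural: the eCRF record covers 32 terms, and the overall incidence would be the incidence of those terms. The number of SAEs that would be lost is unknown.

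The conclusion assumes that the Section 15.5 tables are built from the REDCap export described in Section 16.1, and that no SAE form exists outside the documents. If a separate SAE form or a charter provision is already in use, the remedy reduces to stating it in the protocol.

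**What to change.** - **Sections 14.2.1 and 14.2.4:** restrict the closed list to non-serious AEs. State that every SAE is entered in the eCRF with a verbatim term, whether or not it is listed.
- **Section 15.5:** tabulate all SAEs by treatment group from that record, and label the remaining summary as listed (solicited) AEs, so that its overall incidence is not read as covering everything.
- **Section 14.3:** state that the SAEs in the DSMB report include those outside the list, and check that the charter agrees.
- **Optional:** add erythema and a free-text entry for other events, so that risks named in Section 8.2 without their own term can be recorded.

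The cost is a few sentences of protocol text and one row on the REDCap AE form, plus a small amount of extra data entry and term coding. No new visits or staff are needed. If events have already occurred, retrospective entry would depend on the sites' source documents, which is a reason to make the change early.

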14.2.2 Serious Adverse Events

A serious adverse event (SAE) is an AE that results in the following outcomes:

- Death
- Life-threatening AE: Places the subject at immediate risk of death at the time of the event as it occurred. It does not include an AE that, had it occurred in a more severe form, might have caused death.
- Persistent or significant incapacity or substantial disruption of the ability to conduct normal life functions.
- Inpatient hospitalization or prolongation of hospitalization.
- Congenital anomaly or birth defect.
- Important medical events that may not result in death, be life threatening, or require hospitalization may be considered a serious adverse event when, based upon appropriate medical judgment, they may jeopardize the subject and may require medical or surgical intervention to prevent one of the outcomes listed in this definition above.

This determination is based on the opinion of the investigator.

14.2.3 Assessment of Causal Relationship

A medically-qualified investigator must assess the relationship of any AE to the use of study drug, based on available information, using the following guidelines:

- **Not related:** There is no reasonable causal relationship to the investigational product and the adverse event.
- **Unlikely related:** No temporal association or the cause of the event has been identified, or the drug or biologic cannot be implicated.
- **Possibly related:** There is reasonable evidence to suggest a causal relationship between the drug and adverse event.
- **Related:** There is evidence to suggest a causal relationship and the influence of other factors is unlikely.

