2 EXECUTIVE SUMMARY

Title	Vestibulodynia UPDATE: Vestibulodynia: Understanding Pathophysiology and Determining Appropriate Treatments
Indication	Three continuous months of insertional entryway dyspareunia and/or pain to touch/tampon insertion indicated by self-report as well as pain score of "3" or greater on the tampon test during screening.
Locations	Duke University, UNC, UCLA
Brief Rationale	Vestibulodynia (VBD) is a chronic pelvic pain condition that affects 1 in 6 reproductive aged women, yet remains ineffectively treated by standard trial-and-error approaches. Our group has identified two distinct VBD subtypes that may benefit from different types of treatment: VBD peripheral (VBD-p) subtype characterized by localized pain specific to the vulvar vestibule, and VBD central (VBD-c) subtype characterized by pain at both vaginal and remote body regions. Preliminary data further demonstrate that VBD-p and VBD-c subtypes differ with respect to patient reported outcomes (e.g., physical and mental health), production of cytokines (intracellular proteins that regulate the activity of pain nerves and inflammatory processes), and expression of microRNAs (small non-coding RNA molecules that regulate gene expression). Women with VBD-p exhibit normal psychological profiles; balanced circulating pro- and anti-inflammatory cytokines; and dysregulation in microRNAs that regulate the expression of genes in estrogen pathways. In contrast, women with VBD-c report decreased functional status and increased somatization; increased pro- but not anti-inflammatory cytokines; and dysregulation in microRNAs that regulate the expression of genes relevant to muscle, nerve, and immune cell function.
Study Design	Two-center, randomized, double-blind, placebo-controlled 2x2 factorial study enrolling 400 women to participate for 24-week duration.
Treatment	Participants will receive one of four treatments for 16 weeks: 
• 5% lidocaine/0.5mg/ml 0.07% estradiol compound vaginal cream + placebo pill• placebo vaginal cream + nortriptyline pill• 5% lidocaine/0.5mg/ml 0.07% estradiol compound vaginal cream + nortriptyline pill• placebo vaginal cream + placebo pill

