5.3 Baseline Evaluation Phase and Randomization

Immediately following screening, research participants will complete all baseline assessments, including 1) completion of validated questionnaires to measure perceived pain, health, mood, and sexual function 2) vulvar exam and quantitative sensory testing to measure pressure pain thresholds at local (vaginal) and remote body sites, and 3) collection of biologic samples to measure local (vaginal) and systemic (blood) cytokines and miRNAs. The complete schedule of assessments to be obtained during the baseline visit is outlined in **Appendix A**.

Participants who fulfill all the inclusion criteria and none of the exclusion criteria will be randomly assigned on a 1:1:1:1 ratio to one of four treatment groups:

- 5% lidocaine/0.5mg/ml 0.07% estradiol compound vaginal cream + placebo pill
- placebo vaginal cream + nortriptyline pill
- 5% lidocaine/0.5mg/ml 0.07% estradiol compound vaginal cream + nortriptyline pill
- placebo vaginal cream + placebo pill

Medication assignments will be determined by the Duke Clinical Research Institute (DCRI) using randomized blocks, and then stratified by enrollment site. The DCRI will create a SAS program to generate the random sequence that will be loaded in RedCap. Participants and research personnel will be blinded to medication assignment.

[figure not shown]
During the baseline visit, participants will be counseled on optimal study medication administration. Participants will receive a written description of the study with contact numbers of study staff to present to their usual care provider(s).

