8 TREATMENT INTERVENTIONS

8.1 Interventions

Participants will be randomly assigned to one of four treatment groups: 1) peripheral treatment in the form of 5% lidocaine/0.5mg/ml 0.07% estradiol compound cream + placebo pill, 2) centrally-targeted treatment in the form of placebo cream + nortriptyline oral pill (up to 50 mg or highest tolerated dose), 3) combined treatment in the form of 5% lidocaine/0.5mg/ml 0.07% estradiol compound cream + nortriptyline; and 4) placebo cream + placebo pill.

Lidocaine/estradiol cream targets peripheral nerves and tissues affected in VBD; the comparison treatment will be an identical-appearing placebo Moisturel™ cream. Participants will be provided with a diagram and written instructions (see **Appendix B**), detailing how to apply the cream to the vaginal vestibule daily for weeks 1-16. Treatment with lidocaine/estradiol or placebo cream will be terminated at 16 weeks.

Nortriptyline is a centrally-acting tricyclic antidepressant that is FDA-approved for treatment of neuropathic pain. Dosing will begin with one 10 mg pill nightly for week 1, then two 10 mg pills nightly for week 2, three 10 mg pills nightly for week 3, four 10 mg pills nightly for week 4, and five for weeks 5 -16. In the event of side-effects without significant adverse events, participants will be advised to decrease dosage by one pill weekly until a tolerable dose is achieved. Treatment with nortriptyline or placebo pill will be tapered off over weeks 16-18, decreasing the dose by 10 mg every 4 days. Participants will be provided with a list of drugs to avoid that are known to interact with nortriptyline (see **Appendix C**).

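### Each woman takes a cream and a pill, but the plan describes one causality rating for both and does not use the factorial margins for safety

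*Combined protocol and SAP*

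**What the plan says.** All references are to the combined protocol and SAP.

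- **Design.** Section 2 describes a "placebo-controlled 2x2 factorial study enrolling 400 women to participate for 24-week duration", and Section 5.3 has women "randomly assigned on a 1:1:1:1 ratio to one of four treatment groups". In every group a woman receives one cream and one pill, each active or placebo.
- **Causality.** Section 14.2.3 states: "A medically-qualified investigator must assess the relationship of any AE to the use of study drug". Its rating categories refer to the drug or product in the singular. Section 14.2.4 lists the descriptors for each event, among them "severity, outcome, and relationship to study drug". Neither section asks for one rating per product.
- **Safety tables.** Section 15.5 states: "Adverse Events will be summarized by treatment group and will include incidence by term, severity, relationship to study medication". It adds overall incidence irrespective of severity and relationship. It names no risk difference, interval or test. Sections 5.3 and 8.1 use the term treatment group for the four arms. Table layouts for the DSMB are left to a charter (Sections 14.3 and 17.1) that is not in the documents.
- **Expected harms.** Section 8.2 says of the cream: "A mild burning or tingling sensation with application is typical". It also names rare erythema and blistering, and reactions to the compounding base. For the pill it says: "Expected side effects with nortriptyline include drowsiness, difficulty sleeping (insomnia), cloudy thinking, and dry mouth", with hives or rash among the other possible effects.
- **Efficacy, for contrast.** The model in Section 15.2 has a term for each drug and one for their interaction.

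**The concern.** When two products are taken together, a rating of 'related' does not say which one the investigator suspected. In the combined arm both products are active. In a single-drug arm the suspected product may be the placebo one, and Section 8.2 itself expects some reactions to the cream base.

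The event term often points to one product: dry mouth to the pill, burning at the application site to the cream. It does not always do so. Rash and hives are on the list of recorded events in Section 14.2.1, and Section 8.2 gives them for nortriptyline. Erythema from the cream is not a listed term, so a skin reaction to the cream would most naturally be entered as rash or hives too (my reading). For such events, a judgement made at the time about which product was suspected cannot be rebuilt later from an unsplit field.

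The second issue is precision. A factorial trial lets all randomised women inform each product's effect. The plan uses that structure for efficacy and writes nothing equivalent for safety.

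**Working it through.** **The plan's own figures.** The plan states no precision for any safety comparison. Its only figure for one arm against placebo is an efficacy one, a detectable difference of 0.98 (Section 15.6: SD 2.0, alpha 0.0167, power 0.80). With difference = (2.394 + 0.842) × 2.0 × sqrt(2/n), n = 80 per arm gives 1.02, n = 87 gives 0.98 and n = 100 gives 0.915. The figure is therefore consistent with one arm against one arm, at an effective size between completers (20% attrition) and all randomised. It says nothing about harm.

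**Inputs for safety.** 400 women at 1:1:1:1 give about 100 per arm, and about 200 on and 200 off each active product. Section 15.4 bases all analyses on everyone randomised. AE rates are not in the documents, so a range is assumed.

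**Formula.** 95% half-width of a risk difference = 1.96 × sqrt[p0(1−p0)/n + p1(1−p1)/n].

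At 10% vs 20%:
- One arm vs double placebo: 1.96 × sqrt(0.09/100 + 0.16/100) = 1.96 × 0.0500 = 9.8 points.
- Factor margin: 1.96 × sqrt(0.09/200 + 0.16/200) = 1.96 × 0.0354 = 6.9 points.

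| Assumed rates | 100 vs 100 | 200 vs 200 |
|---|---|---|
| 5% vs 10% | ±7.3 | ±5.1 |
| 5% vs 15% | ±8.2 | ±5.8 |
| 10% vs 20% | ±9.8 | ±6.9 |
| 20% vs 30% | ±11.9 | ±8.4 |
| 20% vs 35% | ±12.2 | ±8.6 |

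The ratio is always 1/sqrt(2) = 0.71, so the margin interval is 29% narrower. With 20% attrition (80 vs 80 and 160 vs 160), the 10% vs 20% row becomes 11.0 and 7.7 points. If an event is never seen, the one-sided 95% upper bound, 1 − 0.05^(1/n), is 2.95% with 100 exposed and 1.49% with 200.

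**Where the gain is smaller.** The table supposes that the other product does not affect the event. Suppose instead that each product adds 10 points, so that the arms run at 10%, 20%, 20% and 30%. Each margin then compares 15% with 25%, and the half-width is 1.96 × sqrt[(0.1275 + 0.1875)/200] = 7.8 points. Against 9.8 that is about 21% narrower.

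**The causality field.** No arithmetic applies. Two active products are confounded only in the combined arm, about 100 women, and mainly for terms both can cause. In the two single-drug arms the ambiguity is between an active product and a placebo one.

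**The case against.** Several stronger conclusions are tempting, and the documents do not support them.

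- *Harm is never attributed to cream or pill.* It is. Cream-only against double placebo, and pill-only against double placebo, give each product's excess incidence by randomisation. Section 15.5 plans incidence by term in each group regardless of relationship, so no investigator rating is needed.
- *The planned risk estimates use half the women.* No comparative safety estimate is planned. A comparison of one arm with double placebo would use 200 of 400, but that describes something a reader might do with the table.
- *No event in any of the 400 women can be assigned to a product.* Many listed terms point to one product, and after unblinding three of the four arms have at most one active product.
- *The DSMB sees a weaker signal.* Its tables are set in a charter that is not available, and Section 14.3 lets its chair ask for more.

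Three further objections have force:

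- 'Study drug' is used collectively elsewhere (Section 8.3), and the eCRF page for AEs is not in the documents. A single field is the natural reading of Sections 14.2.3 and 14.2.4, but it is not proven.
- The rater is blinded, so a split rating would not by itself separate active from placebo. It could, however, be set against actual assignment after unblinding, which an unsplit one cannot.
- The margins can be summed from four-arm counts of women with each event. The table request therefore concerns prespecification and needs no new data.

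**Conclusion.** The point stands as a low-cost improvement and not as an error that undermines the safety data. Two things are missing from the text: a causality rating by product, and a safety summary by factor margin. The first is the more urgent, because it has to be collected as events occur.

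The gain in precision is 29% in interval width for events the other product does not affect, or 6.9 against 9.8 points at the assumed 10% and 20%. It is smaller where both products contribute. These figures rest on assumed AE rates, equal arms of about 100, and no interaction between the products on harm. That last assumption should not be taken for granted, since Section 18.3.4 theorises synergy between the two treatments. No efficacy result and no planned randomised comparison changes.

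**What to change.** 1. In Sections 14.2.3 and 14.2.4 and on the eCRF, have the investigator record relationship twice for each event: once for the cream, once for the pill. If the eCRF already does this, amend the two sections to say so.
2. In Section 15.5, add for each listed AE the incidence and the risk difference with its 95% interval by factor margin: nortriptyline vs placebo pill, and active vs placebo cream, each about 200 vs 200. Place these beside the four-arm table.
3. Keep the four-arm table and state that it is there to show any excess with the combination.

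The cost is one extra eCRF field per event and one extra set of tables. Visits and sample size do not change. The statistical downside is that a margin averages over any interaction on harm and could dilute an excess confined to the combined arm, which is why the third item is needed.
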